## 6.2 IMPs, Formulations, and Strengths

IMPs for this trial will not be supplied directly by Lundbeck. Medications for this study will be obtained using pharmacy voucher cards. These cards will allow for study-specific advanced preventive medications to be obtained from the local pharmacy without cost; the voucher cards will not be used for any other medications including acute migraine treatments. Study-specific voucher cards will be used to cover the cost of any study-specific advanced preventive medications, provided it is used per the FDA approved label.

After randomization is complete, study site personnel will need to obtain the first dose of medication to be administered to the participant during the Baseline Visit (Visit 2).

Participants who will be using subcutaneous anti-CGRP injectables will be instructed on how to use the voucher card at the retail pharmacy of their choice to cover the cost of their anti-CGRP medication throughout the study. For participants assigned to Botox or eptinezumab, study staff will need to obtain these medications using the voucher cards prior to Visit 5 to ensure the medication is available for administration during the visit.

The IMPs to be used in this study are:

**Eptinezumab** – Participants allocated to the eptinezumab arm will begin treatment using eptinezumab which is available as a 100 mg/mL or 300 mg/mL solution, as per the product label. The first dose will be given at baseline during visit 2 and the second dose will be given during visit 5 at week 12 (see [Panel 4](#)).

**OnabotulinumtoxinA** – Participants allocated to Botox will be given the first dose at baseline during visit 2 and the second dose will be given during visit 5 at week 12 (see [Panel 4](#)). Botox will be given as per the product label for the treatment of migraine.

**Erenumab** – Participants will be trained to self-administer the first dose at baseline during visit 2, and then will self-administer doses 2-6 monthly as per the product label. Participants will be given a voucher card to obtain follow-up doses of this medication for the next 5 months. Erenumab will be given as per the product label for either the 70 mg or 140 mg doses. Note that this protocol defines the term, “monthly” as every 28 days.

**Fremanezumab** – Participants will be trained to self-administer the first dose at baseline during visit 2. Following the baseline dose, the participant will either administer 225 mg monthly for months 2 – 6 or administer 675 mg 3 months after the baseline dose (quarterly). Participants will be given a voucher card to obtain follow-up doses of this medication either for the next 5 months or for 1 additional refill 3 months post-baseline. Fremanezumab will be given as per the product label. Note that this protocol defines the term, “monthly” as every 28 days, and “quarterly,” as every 84 days.

**Galcanezumab** – Participants will be trained to self-administer the first dose at baseline during visit 2. At the advisement of the provider, participants may receive a 240 mg loaded dose at baseline followed by monthly doses of 120 mg for months 2 - 6. Participants will be given a voucher card to obtain follow-up doses of this medication for the next 5 months. Galcanezumab will be given as per the product label. Note that this protocol defines the term, “monthly” as every 28 days.

### **6.3 Method of Assigning Participants to Treatment**

Each participant will be assigned a unique study ID by the EDC system, and that number will be used to identify that patient throughout the study. Although assignment of treatments to patients will be randomized, all treatments will be open-label; there will be no blinding to treatment received. The randomization scheme for assigning participants to one of the treatment arms is illustrated in [Figure 1](#).

#### **6.3.1 Change in Treatment**

Participants may switch to an alternative preventive treatment in either treatment cohort after they have received their initial treatment with the medication to which they were randomized. Such a decision may be made upon recommendation of their treating clinician or participant preference. The site staff will investigate the reason for treatment change with both the treating clinician and participant. The use of medications, including gepants, for relief of acute migraine symptoms in either treatment arm is permitted and will be recorded in the smartphone application.

For all participants, the treatment to which they are initially assigned must be the treatment given at Baseline (Visit 2). Switching of medication is not permitted prior to administration of the first dose of medication. For participants who receive eptinezumab or Botox as their initial treatment and elect to switch to a subcutaneous anti-CGRP injectable (i.e., erenumab, fremanezumab or galcanezumab), they may not do so until week 12 (visit 5), after the treatment window for their initial treatment has ended. Participants who receive eptinezumab or Botox at week 12 (Visit 5) will not be permitted to switch their treatment for the remaining duration of the study.

Participants initially treated with a subcutaneous anti-CGRP injectable may only switch to eptinezumab, or Botox at week 12 (visit 5) due to the design of the study. However, these participants may switch to another of the subcutaneous anti-CGRP injectable medications at any time, once the treatment window for their previous injection has ended.

No changes in treatment will be permitted after Visit 7.

All changes in treatment are to be documented in the eCRF.

If a participant wishes to switch their medication, but does not meet the specified criteria to do so, as stated above, they should be withdrawn from the study and be treated as per standard of care by their physician.

## 6.4 IMP Accountability

Treatment type, along with the date(s) on which treatments are administered, will be recorded in the eCRF.

The investigator and the pharmacist (if applicable) must agree to only dispense study-specific IMP to participants enrolled in the study. The investigator or the pharmacist (if applicable) must maintain an adequate record of the receipt and distribution of the study-specific IMPs that they obtain for study participants (see [Section 6.2](#)). This record must be available for inspection at any time.

## 7 Concomitant Medication

Concomitant medication is any medication other than the IMPs that are taken during the study from Screening up until the participant completes the study at Visit 8. This includes all prescription and over-the-counter medications, as well as vitamins and supplements. In addition, if a patient receives a COVID-19 vaccination while enrolled in the trial, each dose of the vaccine received should be entered as a concomitant medication.

Details of all concomitant medication being taken at the time of the Screening Visit must be recorded in the eCRF at the first visit. Any changes (including reason for changes) in concomitant medication must be recorded at each subsequent visit.

For any concomitant medication for which the dose was increased due to worsening of a concurrent disorder after enrollment in the study, the worsening of the disorder must be recorded as an adverse event and the medication with the increase dosage should be reported as a new concomitant medication.

For any concomitant medication initiated due to a new disorder after enrollment in the study, the disorder must be recorded as an adverse event.

## 8 Study Visit Plan

### 8.1 Overview

An overview of the procedures and assessments to be conducted during the study and their timing is presented in [Panel 1](#), [Panel 2](#), [Panel 3](#), and [Panel 4](#). Details are in section [9](#).

After completing or withdrawing from the study, the patient must be treated in accordance with usual clinical practice.

**Panel 1: eDiary Collected Assessments at Visit 1**

Assessments

• SDM-Q-9

• SURE Test

• PAM-10

**Panel 2: eDiary Collected Assessments at Visit 2**

Assessments

• EQ-5D-5L(a)

• PSS(a)

• MIDAS(a)

• HIT-6(a)

• PI-MBS(a)

• Daily Headache Status Report (see Panel 3 for details)

(a) Collected prior to initial treatment given at Visit 2

**Panel 3: Post-Baseline eDiary Collected Assessments**

Assessments	Reporting Schedule				
	Daily	Weekly (a)	Monthly (b)	Quarterly (c)	Early Termination
Daily Headache Status Report: - Did they have a headache in the previous 24 hours? Y/N	X				X
If answer is “Yes” to “Daily Headache Status” then participants will be prompted to report their Daily Headache Symptoms: - What symptoms did they experience with the headache? - How do they rate the severity of the symptoms? - What was the most “bothersome” of the symptoms (i.e. PI-MBS)?	X				X
If answer is “Yes” to “Daily Headache Status” then participants will be prompted to report their Acute Headache Medication Usage: - What medication(s) did they take (if any) to relieve the headache? - How do they rate the effectiveness of the medication(s) taken?	X				X
If answer is “Yes” to “Daily Headache Status” then participants will be asked if they considered this headache to be a migraine.	X				X
If answer is “No” to “Daily Headache Status” then participants will be prompted to respond to the following: - Do they have any residual symptoms lingering between headaches? - Have they experienced any “warning” symptoms prior to a headache? - What degree of impact did each of these symptoms have?	X				X

Assessments	Reporting Schedule				
	Daily	Weekly (a)	Monthly (b)	Quarterly (c)	Early Termination
Healthcare Resource Utilization	X (d)				X
EQ-5D-5L		X			X
Good Day/Bad Day Scale		X			X
PSS			X		X
HIT-6			X		X
PAM-10				X	X
MIDAS				X	X
SDM-Q-9				X	X
TSQM				X (e)	X

(a) Weekly = every 7 days, Visit 2 date = Day 0 (b) Monthly = every 28 days, Visit 2 date = Day 0

(c) Quarterly = every 84 days, Visit 2 date = Day 0 (d) Will be assessed 3 times per week

(e) Assessed at Day 168 only

**Panel 4: Assessments Administered via Site staff**

Study procedures	Screening Visit	Baseline Visit	Monthly Follow-Up	Monthly Follow-Up	Monthly Follow-Up	End of Treatment / Early Termination	Safety Follow-Up
		Day 0	Days 28 & 56 (+/- 3 days)	Day 84 (+/- 3 days)	Days 112 & 140(+/- 3 days)	Day 168 (+ 7 days)	56 days (+/- 5 days) after End of Treatment / Early Termination
	Visit 1	Visit 2	Visits 3-4 (f)	Visit 5 (g)	Visits 6-7 (f)	Visit 8 (f)	Visit 9
Written informed consent	✓						
Review inclusion and exclusion criteria	✓	✓					
Demography	✓						
Medical history inclusive of migraine, psychiatric, cardiac and family medical history	✓						
Vital signs	✓						
Concomitant medications and use of tobacco products	✓	✓	✓	✓	✓	✓	
Adverse events (continuous monitoring) (a)	✓	✓	✓	✓	✓	✓	✓
Adverse drug reactions (continuous monitoring)		✓	✓	✓	✓	✓	
Administration of Decision Guide	✓						

Study procedures	Screening Visit	Baseline Visit	Monthly Follow-Up	Monthly Follow-Up	Monthly Follow-Up	End of Treatment / Early Termination	Safety Follow-Up
		Day 0	Days 28 & 56 (+/- 3 days)	Day 84 (+/- 3 days)	Days 112 & 140(+/- 3 days)	Day 168 (+ 7 days)	56 days (+/- 5 days) after End of Treatment / Early Termination
	Visit 1	Visit 2	Visits 3-4 (f)	Visit 5 (g)	Visits 6-7 (f)	Visit 8 (f)	Visit 9
Randomization to treatment arm	✓ (d)						
Participant training on eDiary	✓						
Participant training on CGRP administration (b)		✓					
Administration of Treatment		✓ (e)		✓ (h)			
Infusion Satisfaction Survey (c)		✓		✓			
Provide instructions to obtain additional doses of CGRP (a)		✓					
Review eDiary use		✓	✓	✓	✓		
Healthcare Resource Utilization		✓	✓	✓	✓	✓	
eDiary close out						✓	

(a) AE monitoring begins upon signing ICF

(b) Only for participants in CGRP arm

(c) Only for participants receiving eptinezumab treatment; completed using paper questionnaire

(d) will need to be performed by site after participant qualifies in order for site to be prepared for appropriate treatment at Visit 2

(e) eptinezumab infusion, Botox or CGRP

(f) Conducted via telephone or videoconference

(g) Conducted on site only for participants receiving Eptinezumab infusion or Botox; conducted via telephone or videoconference for those in CGRP group

(h) Eptinezumab infusion or Botox, those receiving subcutaneous anti-CGRP medications are also encouraged to attend in person (see section 8.6 below).

## **8.2 Screening Visit (Visit 1)**

Screening assessments are to be conducted within 21 days of the participant's initial treatment at the Baseline Visit (Visit 2) to allow the investigator sufficient time to review the participant's medical history and determine if the participant is eligible for study participation.

The Investigator, or qualified designee, will conduct the following procedures at this visit and record the data in the eCRF:

- Conduct of Informed Consent procedures
- Assignment of participant identification number (automatically assigned by EDC system)
- Review of inclusion and exclusion criteria
- Demography
- Medical history
- Includes migraine history, psychiatric history, cardiac history and family migraine history
- Vital signs
- Concomitant medications and use of tobacco products
- Review of AEs
- Download smartphone app to participant's phone or tablet
- Participant training on use of eDiary
- Administration of Decision Guide

Participants who provide consent and are confirmed by site study staff to be eligible will be provided with the following PROs at the time of screening for completion via their eDiary:

- SDM-Q-9
- SURE test
- PAM-10

In addition, participants will complete the Daily Headache Status Report beginning with the screening visit.

Re-screening of patients who screen fail will be allowed.

## **8.3 Process for Randomization to Treatment Arms**

Participants will be randomized to their respective treatment arms after determining eligibility to participate at the Screening Visit and prior to Baseline (Visit 2). Randomization will be completed in the EDC system. Participants with episodic migraine will be randomized to eptinezumab or SC CGRP (i.e. erenumab, fremanezumab or galcanezumab) in a 1:1 manner. Those experiencing chronic migraine will be randomized to eptinezumab, SC CGRP, or Botox in 3:2:1 manner. Participants randomized to the SC CGRP injectable arm will be free

to select treatment with any anti-CGRP injectable of their choice (i.e. erenumab, fremanezumab or galcanezumab). Please see [Figure 1](#) for further details on the randomization design.

#### **8.4 Baseline Visit (Visit 2)**

This visit is to occur within 21 days of Visit 1. Prior to the participant arriving for the Baseline Visit, the treatment arm for the participant will need to be determined, and the first dose for administration will need to be obtained.

At the time of the Screening visit, the participant, with assistance from the site, will record the expected date of the Baseline visit within the app. This date can be modified, as needed, to accommodate rescheduled appointments within the allowable 21-day window from Screening to Baseline. On the day of Baseline, the app will notify the participant to complete their Baseline PROs. Prior to treating the participant, the site will confirm the completion of the Baseline PROs.

On the day of the visit, the participant will complete the following assessments in their eDiary prior to initiation of treatment (see [Panel 2](#)):

- EQ-5D-5L
- PSS
- MIDAS
- HIT-6
- PI-MBS

The participant will also complete the Daily Headache Status Report in their eDiary on this date. This may occur before or after the visit, depending on the time of the visit.

The Investigator, or qualified designee, will conduct the following procedures at this visit and record the data in the eCRF:

- Review of inclusion and exclusion criteria (prior to treatment)
- Review of AEs (prior to treatment)
- Review of concomitant medications and tobacco use (prior to treatment)
- Review of eDiary use
- Review Healthcare Resource Utilization
- Participant training on self-injections of subcutaneous anti-CGRP mAbs (for participants assigned to this treatment arm)
- Administration of first treatment
- Infusion Satisfaction Survey (post-treatment; for participants receiving eptinezumab only)
- Review of ADRs (starting after treatment administration)
- Provide instructions for how to obtain additional doses of subcutaneous anti-CGRP injectables to participant for future use (for participants assigned to this treatment arm)

- Review participant instructions until next visit
- Schedule next visit

Administration of the first treatment will consist of either the participant's first treatment with eptinezumab or Botox or the participant's first injection of a subcutaneous anti-CGRP mAb. For participants in the subcutaneous anti-CGRP arm, the first dose should be self-administered by the participant under the supervision of the site staff.

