## **Appendix IX**

### **Good Day / Bad Day Scale**

#### **Good Day / Bad Day Scale**

Over the past week, please indicate the total number of *good days* and *bad days* you have had.

The total for both days must add up to 7.

Good days: \_\_\_\_\_

Bad Days: \_\_\_\_\_

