11.2 Analysis Methodology for the Exploratory Endpoints

11.2.1 Estimand for the Number of Good Days (Week 1-4, 1-12, and 1-24) and Exploratory Endpoints

A summary of the intercurrent events that will be addressed and the estimand attributes can be found below.

The estimand is the difference in the mean weekly number of good days within each specified time interval between eptinezumab compared to other advanced preventive therapies (erenumab, fremanezumab, galcanezumab, or onabotulinumtoxinA) in adults with migraine on concomitant acute migraine therapy who have failed ≥ 2 prior oral preventive therapies and who are naïve to advanced migraine therapy based on a treatment policy strategy in which patients are analyzed according to the randomized group and are included in the analysis regardless of discontinuation or switching of the index migraine therapy during the follow-up period.

Intercurrent events that will be addressed include:

- Discontinuing the index preventive migraine medication with or without initiation of a new preventive therapy (i.e., a treatment switch).
- Withdrawal from the study due to lack of efficacy, adverse event, participant request, physician request, or loss to follow-up.
- Interruption or termination of infusions.

Attributes of the estimand for the number of good days include:

- The index treatment of interest is eptinezumab (100 mg or 300 mg) compared to other advanced preventive therapies (erenumab 70 mg or 140 mg, fremanezumab 225 mg or 675 mg, galcanezumab 120 mg, and onabotulinumtoxinA 155 units)
- The population is all patients with migraine who fulfil the inclusion and exclusion criteria.
- The primary endpoint of interest is the mean number of good days across weeks 1-12 after randomization
- The population-level summary is the mean difference between eptinezumab and other advanced preventive therapies for the endpoint

Estimands for the remaining exploratory endpoints can be formulated similarly to the estimand for the number of good days described above.

EQ-5D (weeks 1-4, 1-12, and 1-24)

- The endpoint to be obtained is the weekly EQ-5D score in each specified time interval
- The population level summary is the difference in mean weekly EQ-5D score in patients on eptinezumab relative to advanced migraine therapies in each time interval

PI-MBS (weeks 1-4, 1-12, and 1-24)

- The endpoint to be obtained is the weekly most bothersome symptom and associated severity

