18.3 Good Day/Bad Day Scale (Week 1-4, 1-12, and 1-24)

The Good Day/Bad Day Scale measures patients’ global perception of the effect of symptoms on the life of people living with migraine by asking how many “good days” and “bad days” they had over the past week. The total number of days reported is required to total 7 (i.e, the sum of the number of good days and bad days must equal 7).

The Good Day/Bad Day scale is reported weekly. If the total number of days reported is <7 for a given week, then the number of good days will be considered as missing. Missing values will be imputed using multiple imputation methods based on the amount and pattern of missing data.

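### The Good Day/Bad Day scale is not collected before the first dose, so the good-days model lacks a baseline of its own outcome and loses precision

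*Protocol*

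**What the plan says.** SAP 11.2.1 writes out one estimand in full, for good days, and states: "The primary endpoint of interest is the mean number of good days across weeks 1-12 after randomization". Protocol 3.3 says there is no primary objective, and SAP Panel 1 lists good days among the exploratory endpoints.

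The pre-dose collection lists are these:

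- **Screening (Protocol Panel 1 and 8.2).** Eligible participants "will be provided with the following PROs at the time of screening for completion via their eDiary": SDM-Q-9, SURE and PAM-10. The Daily Headache Status Report also starts here.
- **Visit 2, pre-dose (Protocol 8.4 and the panel titled "Panel 2: eDiary Collected Assessments at Visit 2").** In 8.4, "the participant will complete the following assessments in their eDiary prior to initiation of treatment": EQ-5D-5L, PSS, MIDAS, HIT-6 and PI-MBS.

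Good Day/Bad Day is scheduled only in "Panel 3: Post-Baseline eDiary Collected Assessments", in the weekly column, with the footnote "Weekly = every 7 days, Visit 2 date = Day 0". The form in Appendix IX asks about a one-week recall: "Over the past week, please indicate the total number of" good and bad days.

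The good-days MMRM in SAP 11.2.2 contains week, treatment, their interaction, and any covariates found to differ significantly between the arms. Neither the candidate list in SAP 11.2.8 nor Appendix I includes a pre-treatment good-days count.

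**The concern.** The trial enrols people from high-frequency episodic migraine through chronic migraine, so good days per week before treatment probably vary a good deal from person to person. A pre-treatment value of the outcome is usually the strongest single covariate available. Without it, stable between-person differences in good days stay in the residual variance of the mean comparison, and the arms cannot be compared at baseline on the scale itself.

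The plan accepts this principle elsewhere. The HIT-6 and MIDAS models carry a baseline level, and the illustrative migraine-day regression in SAP 15.1 includes migraine days from the month before screening. The good-days model has no counterpart. With the sample size set by budget at 100 per arm (SAP 15.1), a covariate is one of the few cheap sources of precision.

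**Working it through.** **1. Is there any pre-dose report?** Setting the schedules side by side:

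| Instrument | Screening (Panel 1, 8.2) | Visit 2 pre-dose (Panel 2, 8.4) | Post-baseline (Panel 3) |
|---|---|---|---|
| Good Day/Bad Day | no | no | weekly |
| EQ-5D-5L | no | yes | weekly |
| HIT-6 | no | yes | monthly |
| MIDAS | no | yes | quarterly |

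Counting every 7 days from Day 0 puts the first Good Day/Bad Day report at Day 7. With one-week recall it covers the first week on treatment. One could try to read a Day 0 report into the weekly footnote, but EQ-5D-5L sits in the same weekly column and is still listed separately in Panel 2. The weekly schedule is therefore not what supplies a Day 0 value.

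**2. Does the plan give a figure for good days?** No. SAP 15.1 says good preliminary data on the PROs are lacking. Its power table (Panel 6) is for migraine days. As a check on that table, power = Φ(SES × √(n/2) − 1.96). With SES 0.36 and n = 100 per arm this is Φ(2.546 − 1.96) = 72.1%, matching the stated 72%.

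**3. Size against a wholly unadjusted model.** Let r be the correlation between baseline and the post-treatment mean. It is an assumption, since the documents give none.

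- SE reduction = 1 − √(1 − r²)
- Equivalent sample-size factor = 1/(1 − r²)

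| r (assumed) | 1 − r² | SE reduction | Equivalent extra participants |
|---|---|---|---|
| 0.4 | 0.84 | 8% | 19% |
| 0.5 | 0.75 | 13% | 33% |
| 0.6 | 0.64 | 20% | 56% |
| 0.7 | 0.51 | 29% | 96% |

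Purely as illustration, borrowing the migraine-day SES of 0.36 and dividing it by √(1 − r²) moves 72% power to 79%, 84%, 89% and 95% at these four values.

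**4. Is that range of r plausible?** Under compound symmetry with week-to-week correlation ρ, one baseline week correlates with a 12-week mean at r = ρ/√(ρ + (1 − ρ)/12).

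- ρ = 0.3: 0.3/√0.358 = 0.50, a 13% SE reduction.
- ρ = 0.5: 0.5/√0.542 = 0.68, a 27% SE reduction.

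This assumes that the correlation across the start of treatment equals the on-treatment correlation. Varied treatment response would lower it.

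**5. Gain beyond proxies.** Suppose, as an assumption, that covariates already collected explain R² = 0.16 and that adding baseline good days raises this to 0.25. The extra SE reduction is 1 − √(0.75/0.84) = 5.5%, compared with 13% against no adjustment.

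**6. The interaction test.** SAP 11.2.2 tests treatment by week. Under compound symmetry, the covariance of baseline with a contrast between weeks s and t is ρσ² − ρσ² = 0. Stable person differences cancel, so the covariate adds essentially nothing to that test. Step 3 therefore applies to the mean differences over weeks 1-4, 1-12 and 1-24, which are the population-level summaries.

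**The case against.** A reader might infer that the good-days comparison is biased, or that no pre-treatment information bears on it and imbalance could go entirely unseen. The documents do not support either reading.

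- **Bias.** A randomized comparison of post-treatment values is unbiased without a baseline.
- **EM/CM mix.** Randomization is within strata. It is 1:1 in EM; in CM the 3:2:1 ratio gives 3 for eptinezumab against 2 + 1 = 3 for the pooled comparators, again 1:1. That source of heterogeneity is balanced by design, leaving within-stratum variation.
- **Proxies.** Migraine days in each of the prior three months, migraine class, daily headache reports from screening, and Visit 2 EQ-5D-5L and HIT-6 all precede treatment. SAP section 7 summarizes baseline migraine days by group.
- **Status.** The study is exploratory, and the Protocol frames good days as a difference between groups, not as change over time.
- **Collecting a baseline is not enough.** EQ-5D-5L has a pre-dose value, yet its MMRM has no baseline term either.

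All of this stands and limits the weight of the point. It does not remove it. SAP 11.2.2 commits to none of these proxies, because a covariate enters only if it differs significantly between the arms. Visit 2 EQ-5D-5L and HIT-6 and run-in headache frequency are not on the 11.2.8 candidate list at all. The SAP also treats the link between migraine days and good days as something to explore (11.2.7), so how well a proxy would work is unknown.

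**Conclusion.** The omission is confirmed: no document schedules a Good Day/Bad Day report before the first dose. The cost is precision on the mean difference in good days, and a balance check on the scale itself. Validity is not at stake.

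The 8% to 29% SE reduction rests on an assumed r of 0.4 to 0.7 and on comparison with a model that adjusts for nothing. It would be wrong to read it as the gain over what the trial already collects, which would be smaller, or as a gain for the treatment-by-week test, which under compound symmetry would be slight. This is a worthwhile, inexpensive improvement to the endpoint that the SAP puts first, and the sponsor should make it.

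**What to change.** Add the Good Day/Bad Day scale to Protocol Panel 1 and section 8.2, completed in the app at screening after eligibility is confirmed and before randomization. Enter that value as a pre-specified fixed covariate in the good-days MMRM (SAP 11.2.2), whatever the balance tests show, and list it in SAP 11.2.8 and Appendix I.

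Timing involves a trade-off. Screening may precede dosing by up to 21 days, so a one-week recall could reach back to days −28 to −21. Visit 2 is closer to dosing but comes after allocation in an open-label study, where knowledge of the arm could colour the answer. The scale may be repeated with the Visit 2 pre-dose PROs, but the model covariate should be the pre-randomization value.

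For participants enrolled before the change, or for everyone if enrolment is complete, pre-specify baseline migraine days or run-in diary clear days (SAP 3.5.3), together with EM/CM stratum, as fixed covariates. Run-in length varies, so clear days should enter as a proportion of reported days.

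Cost: a minor amendment and app change for one item with two numbers, at a visit where three app questionnaires are already completed. Participants already enrolled will lack the value.
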